### Interventions and Duration

There are two phases to the intervention: in-hospital and during post-acute care (PAC) stay (Figure 1: Phases 2 & 3). The hospital phase of the intervention includes identification of medications for deprescribing, a patient preference interview, and discussion with patients' primary treatment teams (outpatient and inpatient). At the point of hospital discharge, the intervention continues at the PAC facility via warm hand-off and weekly monitoring calls by the study team. The intervention ends at PAC discharge, and participants will be contacted for follow-up assessments at 7, 60, and 90 days after PAC discharge.

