Exclusion Criteria: (1) The patient’s primary language is listed on the patient screening panel; any patient with a primary language other than English is excluded. (2) The patient’s case management or social work intake assessment is reviewed to confirm the patient has a valid telephone number and is not homeless, incarcerated or a long-term care resident of a nursing home. In the instance the EMR is unclear, the patient’s social worker or case manager is contacted to confirm. (3) The EMR is reviewed for life expectancy of less than 6 months by searching key terms ‘hospice’ and ‘stage 4’ to find referrals to hospice care or notes indicating the patient has a stage 4 metastatic cancer, which would exclude them from participation. (4) The ‘research’ tab of the EMR is reviewed to determine if the patient is on another drug trial that excludes them. (5) Finally, the chart is reviewed for any indication the patient will be discharged in less than 48 hours (i.e., presence of transfer orders, etc.), which would not allow the study team sufficient time to complete assessments or the intervention.

After it is determined the patient meets all of the above inclusion criteria and is demographically eligible, the study team reviews the social work referral system (AllScripts or AIDEN) to determine if the patient has a referral to one of the 22 partner SNFs or IPRs. If the patient has no referrals, the coordinator will continue to monitor in case a partner referral is made.

For patients who have multiple hospitalizations during the trial period, they are re-screened at each admission to determine eligibility for enrollment unless they were previously enrolled in the trial.

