2. If a patient is interested in participation but unable to pass the evaluation to self-consent and a surrogate is not present at the hospital, with the patient’s permission, key study personnel will call the surrogate to explain the study and address any questions. A member of the study team will send the surrogate a link to the REDCap consent form for the surrogate to review and sign. The surrogate will also be provided with key study personnel contact information in case they have additional questions. Upon completion of e-consent, surrogates will be able to download a pdf copy of the consent, and key study personnel also print a copy of the signed e-consent and deliver to the patient’s room.
3. *During COVID-19 restrictions, the electronic consent process was used for patients who were on isolation precautions.*

All enrolled patients have an alert placed in their medical record to identify them as a study participant, along with a brief study description and contact information for the study personnel (e.g., study coordinator and PI). Additionally, the study team enters an Informed Consent note utilizing VUMC’s EMR template to indicate time of consent, IRB number, staff member consenting, patient or surrogate who signed consent, and who witnessed the consent. Upon enrollment, the participant is added to an EMR panel for enrolled patients.

Following enrollment, patients will be randomized into the intervention or usual care control group (see Randomization in the Data Analysis section) using the REDCap randomization feature wherein the randomization schedule is uploaded then automatically assigns allocations to authorized users. Participants will be randomized in a 1:1 ratio using permuted blocks of two or four, where the size for each block is selected uniformly at random. This type of randomization ensures balance across the intervention and control groups after every second or fourth randomization (depending on the size of the current block). This randomization scheme will be generated by computer using the Mersenne-Twister pseudo random number.

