## Final Hospital Deprescribing Actions

The final in-hospital phase of the deprescribing protocol requires that the study PharmD or NP assimilate the data from all three phases (Figure 3. 2a, 2b, 2c) to finalize deprescribing actions. Deprescribing can begin at any time after randomization and following step 2a – 2c. All deprescribing actions are executed by the inpatient treatment team using recommendations from the study PharmD or NP. Recommendations include input from the intervention team, patient, inpatient treatment team, and the original prescriber(s) when available.

We anticipate that there will be disagreement between clinical reviewers, inpatient teams, primary prescribers and patients. The incidence and nature of the disagreement will be monitored closely. In anticipation of disagreement the following guidelines will be in place. First, deprescribing of pre-hospital medications will not be recommended to the treatment team (acute or post-acute) without patient agreement. Deprescribing of medications will be recommended against a patient's preferences when there is a clear indication of imminent safety threats as determined by the intervention pharmacist / NP, inpatient clinical team, or primary prescriber. Otherwise, we will first counsel the patient regarding the rationale for the deprescribing recommendation and seek consensus. If disagreement continues, we will monitor the medication throughout the intervention phase for side effects. In addition, we will highlight this medication at discharge for follow-up by the primary prescriber. All final deprescribing actions will be carried out by the inpatient treatment team.

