## PAC Handover and Ongoing Deprescribing at PAC Facility

Within 24-hours of transition to PAC, a study pharmacist or NP has a phone conversation with a designated PAC provider with prescribing authority (NP or physician) to review the Transfer Medication List, highlight deprescribed medications and the need for medication-specific monitoring. In addition, all medications recommended for deprescribing may not be stopped prior to hospital discharge in the interest of first monitoring symptoms and ensuring safety or due to delayed contact and input from the outpatient prescriber. Medications for additional deprescribing at the PAC may be highlighted during this initial handover and discussed again in weekly follow-up calls while the patient remains in PAC (Phase 3).

Following PAC handover, we initiate a weekly conversation via telephone with the designated PAC provider to review intervention participants' medication administration record (MAR) and any drug withdrawal events. Reasons for modifying the Transfer Medication List during the PAC stay will be discussed and intervened upon as necessary. The intervention also will continue for participants readmitted to VUMC directly from PAC (estimated 20%) and continue upon transfer back to the PAC. The study PharmD or NP may also continue to communicate with the original prescriber/ outpatient provider during the PAC stay to confirm their agreement with medication changes. At the time of discharge from the PAC facility, a final reconciled medication list will be sent to the patient's primary outpatient providers along with suggestions for continued medication management and deprescribing as well as any explanations for other medication changes made.

For analytical and feasibility purposes, the intervention ends at the point of discharge to home. If a patient discharges to home instead of a partner PAC facility, they will be withdrawn from the study and only considered to have one phase of the intervention. For safety reasons, the study team provides their outpatient provider with the final discharge medication list highlighting any symptom monitoring required.

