## Data Analyses

Missing Data: We have extensive preliminary data describing attrition due to mortality which should not differ between the intervention and control groups. However, we cannot exclude the possibility that missing data will be associated with intervention. We will examine the incidence of missing data by group. If imbalances are found, we will implement a series of sensitivity analyses, using multiple imputations, to assess the degree of bias that might be induced by missing data.

Randomization, intent-to-treat, and safety outcomes: Participants will be assigned to the usual care control group or the intervention group in a completely randomized fashion (i.e., without blocking or stratification). The effectiveness of randomization will be assessed by summarizing the balance of baseline demographic and clinical factors across randomization groups. The sample mean, standard deviation, and five-number summary will be used to summarize continuous variables. The count and proportion will be used to summarize categorical variables. All randomized patients who complete Phase 2 (i.e., discharged to a partner SNF) will be included in analyses. We will implement both intent-to-treat and per-protocol analyses.

Repeated measures: Barring study withdrawal or death, each participant will be assessed at multiple time points. We anticipate that such repeated measurements will exhibit correlations across time points. Our statistical plan takes full advantage of this information by using a mixed-effects framework for each analysis. In the event that a mixed-effects technique cannot be implemented, an alternative method will be used and the standard errors of effect estimates will be adjusted using the Huber-White ‘sandwich’ method.

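### The plan promises intent-to-treat, but its only stated analysis set is patients who complete Phase 2, so the efficacy analysis as written is a completer analysis

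*Combined protocol and SAP*

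**What the plan says.** All references are to the combined protocol and SAP.

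- **Analysis set.** Data Analyses, in the paragraph on randomization, intent-to-treat and safety outcomes, states: "All randomized patients who complete Phase 2 (i.e., discharged to a partner SNF) will be included in analyses". The next sentence promises both intent-to-treat and per-protocol analyses. Neither term is defined there or elsewhere.
- **Timing.** Enrollment Procedures: "Following enrollment, patients will be randomized into the intervention or usual care control group". Interventions and Duration labels the in-hospital part of the intervention Phase 2 and the PAC stay Phase 3. Final Hospital Deprescribing Actions: "Deprescribing can begin at any time after randomization", once the preference and provider-input steps are done.
- **Patients who do not reach a partner facility.** PAC Handover and Ongoing Deprescribing at PAC Facility: "If a patient discharges to home instead of a partner PAC facility, they will be withdrawn from the study". They are counted as having had one phase of the intervention.
- **Outcome time points.** Outcomes, Hypotheses 1a-1b, analyzes medication counts at hospital discharge, SNF discharge and 90 days later, with adjustment for the enrollment medication count.
- **Missing data.** Data Analyses concedes that "we cannot exclude the possibility that missing data will be associated with intervention" and offers multiple imputation as a sensitivity analysis if missingness is imbalanced between groups.
- **Mortality.** Safety Analyses plans death rates and Cox models overall and by study phase, with follow-up ending at most 90 days after SNF discharge. Under Safety and Healthcare Utilization Outcomes, patients moved to hospice are withdrawn.

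**The concern.** Intent-to-treat compares the arms as they were randomized. A set defined by an event that happens after randomization does not, if that event depends on the treatment or on what happens to the patient in hospital. Completing Phase 2 is such an event. If the plan is followed literally, a completer analysis could be published as intent-to-treat.

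The loss also reaches a time point at which data should exist. A patient who goes home still has a hospital-discharge medication status, and hospital discharge is a planned time point for the primary outcome. The plan does not say whether that value is used. The imputation step does not clearly cover it either, because nothing says that patients outside the Phase 2 set count as missing.

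For mortality the stake is narrower. Two analysts could reasonably treat deaths after withdrawal differently, and for a patient who never entered a SNF they would have no defined end of follow-up.

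**Working it through.** **1. Order of events.** Randomization takes place in hospital (Enrollment Procedures). The Limitations text under Data Analyses confirms that it precedes hospital discharge, because the PAC destination cannot yet be known. Deprescribing may then start. Only after that does the patient go to a partner facility or elsewhere. Membership in the stated set is therefore decided after allocation.

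**2. The plan's own count.** Inputs from Sample Size and Randomization: 144 per year for four years, and 27.5% lost before day 90.
- 144 × 4 = 576.
- 576 × (1 − 0.275) = 417.6, against 420 stated. This reproduces to rounding.
- The same section also gives 567 as the expected enrollment: 567 × 0.725 = 411.1, also close.

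The 27.5% covers every loss up to day 90. The text does not say how much falls in Phase 2. Figure 1 is said to give sample sizes by phase, but it is not shown in the text reviewed.

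**3. How many randomized patients could fall outside the set.** The non-completion share is assumed, and 576 is taken as the number randomized.
- 5%: 576 × 0.05 = 29
- 10%: 58
- 15%: 86
- 20%: 115
- Ceiling, if all attrition fell in Phase 2: 576 × 0.275 = 158

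**4. Scale of a possible distortion (illustration; all inputs assumed).** Let pC and pI be the non-completion shares in control and intervention. Let r be the ratio of mean medication count in non-completers to that in completers, the same in both arms, with no true effect. Then

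completers-only rate ratio = [1 − pC(1 − r)] / [1 − pI(1 − r)]

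- pC = 0.10, pI = 0.15, r = 0.8: 0.98/0.97 = 1.010
- pC = 0.10, pI = 0.15, r = 1.2: 1.02/1.03 = 0.990
- pC = 0.10, pI = 0.20, r = 0.7: 0.97/0.94 = 1.032
- pC = 0.10, pI = 0.20, r = 1.3: 1.03/1.06 = 0.972
- pC = pI, or r = 1: 1.000

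These use raw means. The planned model adjusts for enrollment count, so r should be the gap that remains after adjustment. If half of the 30% gap were already present at enrollment, the last two extremes would become 0.985/0.97 = 1.015 (r = 0.85) and 1.015/1.03 = 0.985 (r = 1.15).

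For comparison, the pilot contrast (50% versus 25% reduction) is 0.50/0.75 = 0.667. The smallest effect for which power is quoted (27.5% versus 25%) is 0.725/0.75 = 0.967.

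**5. Mortality passages side by side.**
- Notification of Unplanned Healthcare Utilizations and Deaths monitors deaths in every phase for each participant.
- Interim analyses and Stopping Rules words the mortality comparison in terms of patients randomized to each arm.
- Safety Analyses asks for results by study phase, and Phase 2 is the hospital phase.
- The Data Analyses paragraph carries safety outcomes in its heading and contains the Phase 2 rule. Applied to safety, that rule would remove every in-hospital death after randomization and leave the hospital stratum with none.

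The first three agree with each other, and the fourth conflicts with them only if its rule is meant to cover safety. None of the four states how deaths after hospice or home withdrawal are counted or censored, or when follow-up ends for someone with no SNF discharge.

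**The case against.** The strongest reply on efficacy is that the rule says who will be included and does not say that nobody else will be. Screening also limits the loss: patients are recommended for SNF placement, and staff check the referral system to "determine if the patient has a referral to one of the 22 partner SNFs or IPRs". An effect of the intervention on destination is possible but not shown, and the illustration needs completion to differ by ten points between arms to reach its extremes. All of this bears on the size of the problem. It does not supply an all-randomized set, which no section defines.

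The 0.967 comparison is also weak. Under a common standard error, 80% power at 27.5% versus 25% would imply over 99.9% at 30% versus 25%, whereas the plan quotes about 90%. It should not carry the argument.

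A reader might infer that the plan leaves the mortality population open altogether, or drops in-hospital deaths. The documents do not support that: three safety passages point to all randomized patients, and the contrary reading rests on a paragraph heading. A reader might also take person-months of observation to mean censoring at withdrawal. That is a natural reading, but it is not stated.

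Finally, one might argue that the data for withdrawn patients are already in hand, since for those going home "the study team provides their outpatient provider with the final discharge medication list highlighting any symptom monitoring required". That is a safety step in the intervention section and does not show that lists are collected for withdrawn controls. The records release is worded for healthcare utilization, so it should not be assumed to cover deaths after withdrawal.

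**Conclusion.** Wrong as written. The plan promises intent-to-treat but describes a completer or modified intent-to-treat set, fixed by an event after randomization. This conclusion rests on the text alone and needs no assumption about bias.

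The size and direction of any bias cannot be computed from the documents. Under the assumed inputs, the unadjusted distortion lies between about 0.97 and 1.03. The enrollment-count adjustment should reduce it, and it is small beside the pilot effect of 0.667. A reader might infer that the result is biased toward the intervention; nothing in the documents shows that.

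For mortality, the defect is limited to the conflict with the Data Analyses heading and two missing rules: deaths after hospice or home withdrawal, and the end of follow-up for patients who never enter a SNF.

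**What to change.** 1. In Data Analyses, define intent-to-treat as all randomized patients in their assigned arm. Include hospital-discharge medication outcomes for everyone discharged alive, whatever the destination, plus later counts where obtained; the planned mixed model can use partial records. Report in-hospital deaths and Phase 2 non-completion by arm. Keep Phase 2 completers as a supportive or per-protocol set.
2. State that the safety set is all randomized patients from randomization, so that this paragraph agrees with Interim analyses and Stopping Rules and with Safety Analyses.
3. State how deaths known after hospice or home withdrawal are counted or censored in the all-cause mortality analysis. Give an end-of-follow-up date for patients who never enter a SNF, and keep the existing limit of 90 days after SNF discharge for the others. A new common window from randomization is not required.

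The cost is some SAP and protocol wording, and abstraction of hospital-discharge data from the hospital EMR for withdrawn patients in both arms. Later outcomes for those patients will be captured incompletely, so the gain is mainly at the hospital-discharge time point.

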Although the published literature has strongly associated polypharmacy with geriatric syndromes, it is unknown if deprescribing, as defined by medication dose or number reductions, leads to improvements in geriatric syndromes. We prospectively collected data on 904 Medicare patients discharged to SNF and found that 98% met criteria for polypharmacy ( $\geq 5$  medications) with an average 14 and 15 medications at hospital and SNF discharge, respectively. A systematic review was then conducted by clinicians and pharmacists of all discharge medications for 156 of these patients using explicit review criteria to link medication side effects with geriatric syndromes. An average of 5.9 discharge medications per patient was determined to be associated with one or more geriatric syndromes in these patients. We also pilot-tested a patient-centered deprescribing intervention (“Shed-Meds”) wherein we successfully engaged patients and providers to reduce the number or dose of medications prior to hospital discharge. Based on these preliminary data, we propose a randomized, controlled trial to evaluate the effects of the Shed-Meds deprescribing intervention on polypharmacy, geriatric syndromes, and other outcomes during the care transitions from hospital to SNF to home. Our overarching hypothesis is that reducing medications for older patients across the continuum of care will favorably impact geriatric syndromes at home.

**Specific Aim 1:** Implement a patient-centered deprescribing intervention (Shed-Meds) that spans the continuum of hospital and post-acute care to reduce the total number of medications patients are prescribed in each care setting and at home after SNF discharge.

**Hypothesis 1a:** The Shed-Meds intervention will result in a significant increase in the total number of medications deprescribed, as defined by termination or dose reductions, at hospital discharge, SNF discharge and 90 days after SNF discharge.

**Hypothesis 1b:** Shed-Meds will result in a significant reduction in the number of potentially inappropriate medications (PIMs) and medications associated with geriatric syndromes at hospital discharge, SNF discharge and 90 days after SNF discharge.

**Hypothesis 1c:** Shed-Meds will result in a significant decrease in the anticholinergic and sedative drug burden of prescribed medications at hospital discharge, SNF discharge and 90 days after SNF discharge.

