## **STUDY DESIGN**

The study is a 5-year, randomized controlled clinical intervention trial at a singular academic medical center.

Primary Outcomes are change in total number of medications including the number of potentially inappropriate medications, number of medications associated with geriatric syndromes, and medications that contribute to anticholinergic and sedative drug burden.

Secondary Outcome is the impact of deprescribing on prevalence and severity of geriatric syndromes, medication adherence, and functional health status.

Eligible patient population is aged 50 years or older, experiencing polypharmacy as defined by 5 or more home medications, and hospitalized at VUMC with a referral to partner post-acute care facility.

Exclusion criteria include limited life expectancy (less than 6 months), non-English speaking, no telephone, homeless or incarcerated, enrolled in another drug trial, and expected to discharge from VUMC in less than 48 hours.

The primary study setting is Vanderbilt University Medical Center (VUMC), a private, non-profit, tertiary care teaching organization located in Nashville, Tennessee. The medical center is a principal referral center for physicians and patients throughout the Southeast, and it serves a diverse population in terms of income, geography, and education level. We will work with patients discharged to 20 SNFs and 2 IPRs within a nine-county radius of Nashville. The target PACs are all for-profit and comparable to PACs in the middle TN area based on publicly reported staffing and quality indicators ([www.medicare.gov](http://www.medicare.gov)).

The timeline for the study is 5 years with enrollment beginning in March 2017 and enrollment closing at the end of October 2020.

The Shed-MEDS intervention is a multistep deprescribing protocol which considers patient and disease factors, life expectancy, goals of care, and appropriate treatment targets. Medication-specific factors such as drug-drug interactions, drug-disease interactions, and drug-specific safety profiles are also incorporated. Finally, patient preferences and primary prescriber input are key to final deprescribing actions by identifying the medications patients are willing to discontinue and seeking their primary prescriber's agreement. In this intervention, deprescribing is defined as either stopping a medication or reducing the dose/frequency of a medication.

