### Pre-Review (Target Medications for Deprescribing)

[figure not shown]
Following the baseline patient/surrogate interview, a study clinical reviewer (pharmacist, geriatric nurse practitioner, or physician) receives the reconciled total enrollment medication list. Using medical record data only such as the history and physical, lab values, physician notes, etc., reviewers will first identify a Medication – Indication pairing for each medication (i.e., clinical reviewers try to establish an indication diagnosis or symptom which the medication treats). If an indication does not exist, “no indication indicated” is specified. For each medication recommended for deprescribing, the reviewer chooses one of the following actions: (1) Stop prior to hospital discharge without need for monitoring; (2) Stop prior to hospital discharge with symptoms/physiologic monitoring; (3) Stop at specified time point following hospital discharge; (4) Reduce over time with monitoring until medication is stopped; (5) Reduce to lower dose without need for monitoring; (6) Reduce to lower dose with symptoms /physiologic monitoring. Then the clinician selects a de-prescribing rationale, and they may select more than one rationale (i.e., choose all applicable rationales) from Table 2.

All medications, both prescription and OTC including vitamins and herbal supplements, are reviewed for potential deprescribing. Select medication classes will not be under consideration for active deprescribing, which include the following:

- Anti-rejection medications for organ/ bone-marrow transplantation
- Chemotherapeutic medications for the treatment of known solid organ or hematologic malignancy.

The above medications may be deprescribed during the study period; however, it would solely be under the direction and recommendation of the primary treatment team or primary prescriber of the medication.

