Limitations: The proposed intervention will be implemented during hospitalization and will continue during the patient’s SNF stay because there is a high probability that new medications, including PIMs, will be added during these care transitions. However, we acknowledge that new medications also might be added after PAC discharge; thus, we have incorporated intervention components that should, at least partially, mitigate this problem. Specifically, we will communicate with pharmacies and known community providers so that they are aware of the patient’s preferences and final discharge medication list. We also will determine during the 7-day post PAC follow-up if intervention patients are taking medications that were previously stopped but which are still in the home. We will assess changes in medications for both intervention and control patients for 90 days post PAC discharge and, thus, be able to determine if intervention components need to be extended past PAC discharge.

The randomization of patients prior to hospital discharge, as opposed to randomization by PAC discharge location, has numerous advantages and is necessary because it is not possible to determine which PAC a patient

will ultimately go prior to implementing the deprescribing intervention. This approach does, however, increase the risk of contamination because both intervention and control group participants will be discharged to the same PACs; thus, there is a possibility that PAC providers will change their medication practices for control participants as a result of our active monitoring of medication changes for the intervention participants. We will be able to detect such contamination effects by comparing changes in the medication lists from hospital to PAC discharge for both intervention and control groups, with the expectation of fewer changes in the intervention group. We believe the risk for contamination is minimal as there was no evidence of contamination effects in our pilot intervention, and PAC providers will not be asked to actively deprescribe beyond following the deprescribing actions recommended by the research team, many of which will be initiated prior to hospital discharge. Finally, PAC and hospital providers may not be equipped to overcome many of the barriers to deprescribing that will be addressed with our Shed-MEDS protocol.

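### As an undirected count of medication-list changes, the planned contamination check does not discriminate: deprescribing copied into control patients would strengthen the pattern that the plan expects

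*Combined protocol and SAP*

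**What the plan says.** The Limitations paragraphs of the Data Analyses section (Statistical Considerations) accept that individual randomisation with shared facilities allows spillover, in that "PAC providers will change their medication practices for control participants as a result of our active monitoring of medication changes for the intervention participants". The authors state that their means of detecting this is "comparing changes in the medication lists from hospital to PAC discharge for both intervention and control groups". The result they anticipate is given in the same sentence: "with the expectation of fewer changes in the intervention group". They give no size, threshold or test. They do not say whether the comparison is of gross or net changes, or which result would count as contamination.

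Other sections bear on what counts as a change and on what should happen during the PAC stay:

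- Study Design: "deprescribing is defined as either stopping a medication or reducing the dose/frequency of a medication".
- Pre-Review (Target Medications for Deprescribing): the permitted actions include "3) Stop at specified time point following hospital discharge", and also gradual reduction with monitoring until the drug is stopped.
- PAC Handover and Ongoing Deprescribing at PAC Facility: "Medications for additional deprescribing at the PAC may be highlighted during this initial handover", with the topic taken up again in weekly calls.
- Limitations, on usual practice: "there is a high probability that new medications, including PIMs, will be added during these care transitions".
- Overview and Objectives, from the preliminary cohort: "an average 14 and 15 medications at hospital and SNF discharge, respectively".

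**The concern.** Under the protocol's own definition, deprescribing is itself a change to the list. A facility that began to deprescribe in control patients would therefore raise the control arm's number of changes, and the intervention arm would look more clearly like the arm with fewer. On the natural reading, that is the result taken to mean no contamination.

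The same behaviour would pull control medication counts toward those of the intervention arm. That would shrink the contrast in total medications at SNF discharge, and possibly at 90 days, which Hypotheses 1a-1b are meant to estimate. An attenuated effect could then be reported beside a check that appears to rule out one explanation for it.

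**Working it through.** The plan gives no figure for this check, so there is none to reproduce. The question is the direction in which the comparison moves, which simple accounting can settle.

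**Inputs.** All quantities are means per patient from hospital discharge to PAC discharge.

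- A = drugs added and S = drugs stopped in control patients without contamination. The documents' 14 and 15 drugs give A − S = +1.
- I = list changes in the intervention arm.
- c = amount of contamination.
- Assumed, not in the documents: S = 2 (range 1 to 3), I = 2, c = 0 to 2. With S = 2, A = 3.

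**Formulas.** Gap between arms = control changes − I. Control net change = additions − stops.

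- Route 1, c extra stops in controls: gap = A + S + c − I; net = A − S − c.
- Route 2, c additions withheld from controls: gap = A − c + S − I; net = A − c − S.

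**Results for S = 2, A = 3, I = 2.**

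| c | Gap, route 1 | Gap, route 2 | Control net change, either route |
|---|---|---|---|
| 0 | 3 | 3 | +1 |
| 0.5 | 3.5 | 2.5 | +0.5 |
| 1 | 4 | 2 | 0 |
| 2 | 5 | 1 | −1 |

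Both routes reduce the control arm's net change by the same amount, so both dilute the contrast in medication count equally. The gap moves by +1 per unit of c on route 1 and by −1 on route 2. These slopes do not depend on A, S or I. With S = 1 or S = 3 the starting gap becomes 1 or 5, and the directions stay the same.

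**Mixed routes.** With 0.5 extra stops and 0.5 withheld additions, control changes are 2.5 + 2.5 = 5 and the gap is 5 − 2 = 3, exactly as without contamination. The net change is nevertheless 2.5 − 2.5 = 0 instead of +1.

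**No contamination, but planned deprescribing during the PAC stay.** The expected pattern requires I < A + S, here I < 5. If planned stops and tapers added three changes per intervention patient to the assumed I = 2, then I = 5 and the gap is 0. The pattern disappears although nothing has spilled over. The documents give no number for these planned changes, so three is only the amount needed to show the effect.

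**Dose reductions.** A dose reduction changes the list but not the number of drugs. On route 1 it therefore raises the control count of changes without appearing in the net count at all.

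**The case against.** The strongest reply is that the comparison is not blind to contamination. The Limitations text itself expects drugs to be added during care transitions, so a plausible spillover is that providers become slower to add them in control patients too. Control changes would then fall toward the intervention level and the gap would narrow, as route 2 shows. The plan also argues that active deprescribing in controls is unlikely, because facilities are asked only to follow the team's recommendations and may not be equipped to overcome the barriers. It calls the risk minimal, and no decision rule depends on the check.

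Most of this stands. A reader might infer that the check has the wrong sign altogether, or that it can detect no contamination. The documents do not support either inference, since withheld additions would show in the expected direction. A reader might also infer that the plan pools additions with stops. It does not say so: it speaks of comparing lists, and itemised lists would show which drugs were added and which were stopped. If changes means the net count, control-arm stops would appear as a fall from the usual drift of +1. Even so, a small net difference would not separate contamination from a weak intervention effect during the PAC stay, and dose reductions would be missed.

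Reversing the interpretation does not rescue the undirected count. If a wide gap were the warning sign, ordinary additions in control patients would set it off.

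The pilot adds little reassurance on this point. Preliminary Data places its outcome assessment at hospital discharge, so as described it could not show spillover inside PAC facilities.

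**Conclusion.** The check is under-specified. On the undirected reading, its claimed ability to detect contamination does not hold for deprescribing copied into control patients. That route strengthens the expected pattern by one change for each copied stop or reduction, withheld additions weaken it by the same amount, and planned deprescribing in the intervention arm can remove it with no contamination. The directions follow from the protocol's definition of deprescribing and from counting changes without regard to type. The sizes rest on assumed values of S, I and c, anchored only by the average rise from 14 to 15 drugs.

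A reader might go further and conclude that contamination is likely, or that it is the trial's main design weakness. Nothing in the documents shows either. This is a minor point about a supporting check. Its practical consequence is that a reassuring result from the check should not be used to rule out dilution when the treatment effect is interpreted.

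**What to change.** 1. For the interval from hospital discharge to PAC discharge, report additions and stops or reductions separately, by arm.
2. As the contamination check, use control participants only. Model stops or reductions, and separately additions, on the number of intervention participants whom the same facility had already received, with a random intercept for facility and adjustment for calendar period.
3. Report estimates with confidence intervals and treat any trend as suggestive. Prior exposure accumulates over time, so secular prescribing change, the lowering of the age limit after four months of enrolment and the COVID-19 period are rival explanations. With 22 facilities, precision will be limited, and a null result would not prove absence.
4. Replace the assurance that contamination will be detected with a statement of which forms the comparison can indicate and how weakly.

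The cost is a short change to the analysis text and two additional models. Facility, hospital and SNF discharge dates and the PAC discharge list are already collected, both arms follow the same data schedule, and Hypothesis 1a already counts dose reductions as well as stops. The primary analysis, alpha and sample size are untouched.
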